5 GENERAL SPECIFICATIONS

This section details the specifications for summarizing all efficacy and safety endpoints.

Continuous variables will be summarized using descriptive statistics, i.e. n (number of subjects with available data), mean, median, standard deviation, minimum, and maximum. For those measures that are analyzed using change from baseline scores, descriptive statistics will also be presented on observed scores, unless otherwise noted.

Minimum and maximum values will be presented to the same precision as the raw data. Mean and median will be presented to one more decimal place than the raw data. Standard deviation will be

presented to two more decimal places than the raw data. P-values will be presented to three decimal places.

Categorical variables will be summarized using counts and percentages. Unless otherwise specified, percentages will be calculated using the numbers of subjects in the summarized population in each treatment group as denominators. Percentages will be presented with a precision of 1 digit after the decimal.

In this study, subject will enter the efficacy data on dosing and post-dose assessments in an e-diary. The e-diary records the date and time of the first dose and of the second dose and is programmed to assess specific time points and assessments as defined in the protocol based on the timing of the dose as recorded. This data is collected in the e-diary when e-diary is in migraine mode. Specifics of Migraine Mode are as below:

- Migraine Mode – First Dose
 - The e-diary enters Migraine Mode **ONLY** if the subject indicates taking his/her first dose of study medication
 - Post Dose Assessments will be completed using the Migraine Questions button at specific time intervals for up to 48 hours after the subject confirms taking study medication

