11.3 Key Secondary Efficacy Analysis

The key secondary efficacy analyses will test the following:

- The treatment effect, between lasmiditan 200 mg and placebo, of the key secondary efficacy endpoint of MBS-free at 2 hours post-dose.
- The treatment effect, between lasmiditan 100 mg and placebo, of the key secondary efficacy endpoint of headache pain-free at 2 hours post-dose.
- The treatment effect, between lasmiditan 100 mg and placebo, of the key secondary efficacy endpoint of MBS-free at 2 hours post-dose.
- The treatment effect, between lasmiditan 50 mg and placebo, of the key secondary efficacy endpoint of headache pain-free at 2 hours post-dose.
- The treatment effect, between lasmiditan 50 mg and placebo, of the key secondary efficacy endpoint of MBS-free at 2 hours post-dose.

MBS-free is defined as the absence of the associated symptom of migraine (either nausea, phonophobia, or photophobia) at 2-hour post-dose that was identified pre-dose as the most bothersome symptom. Subjects who record that no symptoms were present at baseline will be

excluded from the key MBS analyses. Likewise, subjects who treat a migraine of no (0) severity will not be included in the key analysis of headache pain. Such subjects will also be excluded from the table produced for the sensitivity analysis described in Section 11.5, but not from the programming steps that impute missing MBS data.

Subjects who do not provide a symptom rating at baseline will be considered as follows:

- Subjects who record at least one symptom present at baseline, but who do not designate one as most bothersome, will be treated as if all symptoms present are most bothersome and will be considered MBS-free at any time point post-dose only if all symptoms present at baseline are no longer present at that time point.

Subjects taking rescue medication within the first two hours, or who fail to record a symptom rating at 2 hours, will be assumed to have not achieved MBS-free. Subjects who use other medication prior to the study drug to treat the migraine attack will also be assumed to have not achieved MBS-free.

The counts and percentages of which symptom was chosen as the most bothersome symptom will also be presented.

These analyses will be presented by treatment group, based on the first dose.

Sensitivity analyses, as described in Sections 11.4, 11.5 and 11.6 will also be performed for the key secondary endpoints on the mITT population.

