11.7.1 Headache Pain-Free

The endpoint of headache pain-free will be summarized at the 0.5, 1, 1.5, 3, 4, 24, and 48-hour post-dose time points. This summary will be presented by treatment group for the ITT, mITT, and PP populations, based on first dose.

Subjects who had a mild, moderate, or severe headache at the time of dosing will be the reference subjects for this summary. Subjects missing a headache severity at baseline will not be summarized. Subjects missing a severity assessment at a post-dose time point will not be counted as pain-free.

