11.7.5 Headache Relief

Counts and percentages of the number of subjects with headache relief will be presented at the 0.5, 1, 1.5, 2, 3, 4, 24, and 48-hour post-dose time points. This summary will be presented by treatment group for the ITT population, based on first dose.

Headache relief is defined as experiencing a moderate (2) or severe (3) headache at baseline which becomes mild (1) or none (0) at the summarized time point, or a mild headache at baseline which becomes none at the summarized time point.

Subjects missing a headache severity at baseline or at the summarized time point will not be summarized at that time point.

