11.7.13 Headache Pain-Free After Second Dose

Counts and percentages of the number of subjects who are headache pain-free after second dose will be presented at the 0.5, 1, 2, 4, 24, and 48-hour post second dose time points. This summary will be presented by treatment sequence for the ITT-2nd Dose population, and separately for subjects taking a second dose for rescue or recurrence.

Headache pain-free after second dose is defined as experiencing a mild (1), moderate (2) or severe (3) headache at second-dose baseline which becomes none (0) at the summarized time point after a second dose is taken.

Subjects missing a headache severity at baseline or at the summarized time point will not be summarized at that time point.

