11.7.16 Time to Headache Relief After Second Dose

The time to headache pain-free after second dose will be presented by treatment sequence using a Kaplan-Meier analysis. This summary will be presented for the ITT-2nd Dose population, and separately for subjects taking a second dose for rescue or recurrence who report headache severity of mild (1) or moderate (2) or severe (3) at second dose baseline,.

The number of subjects experiencing headache relief, and the number of subjects censored, will be summarized. The Kaplan-Meier estimates, and 95% confidence intervals calculated using the log-log transformation, of the number of hours for 25%, 50%, and 75% of subjects to experience headache relief will be presented. The Kaplan-Meier estimate, and 95% confidence interval, of the probability of experiencing headache relief will be presented at the 0.5, 1, 2, 4, and 24-hour post second dose time points.

Time to headache relief after second dose will be calculated as:

date/time headache severity is reported as mild (1) or none (0) after second dose –
date/time of second dosing of a headache that was moderate (2) or severe (3) at second-dose baseline

or as

date/time headache severity is reported as none (0) after second dose –
date/time of second dosing of a headache that was mild (1) at second-dose baseline

Subjects who do not report a headache with severity of mild or none, or who report a headache with a severity of mild or none after 24 hours post second dose, will be censored at the time of their last non-missing post second dose headache severity assessment at or before 24 hours. Subjects with missing second dose baseline headache severity will not be considered in time to event analysis for second dose. Subjects who report a headache severity of none (0) at second dose baseline, will be presented in a separate listing as a report at the time of second dose but not included in this time-to-relief analysis.

A figure of the Kaplan-Meier analysis will also be presented.

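### Read literally, the headache-relief tables and the second-dose pain-free table keep subjects with no pain at baseline in the denominator, although those subjects can never count as responders

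*SAP*

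**What the plan says.** **The three tables.**

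- SAP 11.7.5 (relief, ITT population) counts a fall from moderate or severe pain to mild or none, "or a mild headache at baseline which becomes none at the summarized time point". A starting value of none is not covered. The only subjects removed are those without a rating: "Subjects missing a headache severity at baseline or at the summarized time point will not be summarized at that time point".
- SAP 11.7.13 (ITT-2nd Dose population): "Headache pain-free after second dose is defined as experiencing a mild (1), moderate (2) or severe (3) headache at second-dose baseline", followed by a rating of none at the time point. The removal rule is the same and concerns missing ratings only.
- SAP 11.7.15 applies the relief definition to the second-dose baseline, again with only the missing-rating rule.

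**The denominator.** SAP 5 states: "Unless otherwise specified, percentages will be calculated using the numbers of subjects in the summarized population in each treatment group as denominators". The ITT and ITT-2nd Dose definitions in SAP 4 require dosing and a post-dose rating, but no particular baseline severity. SAP 8.5 lists none (0) among the baseline severity categories for both populations, so the plan expects such subjects.

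**How the same subjects are handled elsewhere.**

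- SAP 11.2 leaves them out of the primary analysis. SAP 11.3 repeats this: "subjects who treat a migraine of no (0) severity will not be included in the key analysis of headache pain".
- SAP 11.7.1 (first-dose pain-free): "Subjects who had a mild, moderate, or severe headache at the time of dosing will be the reference subjects for this summary".
- SAP 11.7.6 and 11.7.7 (first-dose time to pain-free and time to relief) censor them at the time of first dose.
- SAP 11.7.14 moves them to a listing. SAP 11.7.16 says that they "will be presented in a separate listing as a report at the time of second dose but not included in this time-to-relief analysis".

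**The concern.** A subject who recorded none at the relevant baseline passes the only removal rule in 11.7.5, 11.7.13 and 11.7.15, because the rating is present. The same subject cannot meet the response definition at any time point. Under the default denominator the subject lowers the printed percentage throughout the table. The table and the time-to-event curve for the same endpoint then rest on different effective subjects.

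The gap reaches beyond three tables. The relief summary is repeated in all seven subgroups in SAP 11.8. SAP 11 also makes logistic regression, with odds ratios and p-values, the default for exploratory efficacy hypotheses. Where that default is applied here, the denominator affects more than a descriptive count.

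The second dose raises a further issue. Severity at that point is measured after randomization and after the first dose has acted, so the share with no pain need not be equal across treatment sequences.

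**Working it through.** The documents give no relief rate, no second-dose response rate and no count of baseline-none subjects, so there is no stated figure to reproduce. The check consists of the rules above, algebra, and assumed inputs.

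**1. Printed rate.** Let a table have N subjects, of whom n0 have baseline none, and let q = n0/N. Let p be the true response rate among subjects with pain.

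- Responders = p(N - n0)
- Printed rate = p(N - n0)/N = p(1 - q)
- With the restricted denominator N - n0, the printed rate is p

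**2. Equal q in both arms** (a reasonable expectation at the first dose, where baseline precedes treatment). The difference becomes (pT - pC)(1 - q). With assumed relief rates of 40% (placebo) and 60% (active):

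| q (assumed) | Placebo | Active | Difference | Odds ratio |
|---|---|---|---|---|
| 0 | 40.0% | 60.0% | 20.0 points | 2.25 |
| 1% | 39.6% | 59.4% | 19.8 points | 2.23 |
| 2% | 39.2% | 58.8% | 19.6 points | 2.21 |
| 5% | 38.0% | 57.0% | 19.0 points | 2.16 |
| 10% | 36.0% | 54.0% | 18.0 points | 2.09 |

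For example, at q=5% the odds ratio is (0.57/0.43)/(0.38/0.62) = 2.16.

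**3. Unequal q** (possible at the second dose). The difference is pT(1 - qT) - pC(1 - qC). If the true rates are equal at p, this reduces to p(qC - qT), so its sign depends only on which sequence has more baseline-none subjects. With an assumed p of 40% in both and shares of 5% and 2%, the table prints 38.0% against 39.2%. That is a spurious 1.2 points against whichever sequence has the larger share.

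**4. Table against curve.** In made-up data on 570 subjects, 30 more were added and censored at time 0 (30/600 = 5%). The Kaplan-Meier estimates did not change: 35.8% at 2 hours, 65.0% at 4 hours and 85.5% at 24 hours, with and without the extra subjects. The crude 2-hour proportion fell from 186/570 = 32.6% to 186/600 = 31.0%. Censoring at time 0 removes these subjects from the estimate, whereas the crude table does not.

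**The case against.** **The literal reading is an inference.** No sentence calls these subjects non-responders, and a programmer could take the response definition as limiting the table to subjects with pain. This stands in part. But 11.7.5 names one departure from the default denominator and not this one, while 11.7.1 and 11.7.16 state the restriction outright. Two programmers following the text could print different percentages.

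**A reader might infer that the relief rates will be too low compared with the pain-free table.** The documents do not settle that. The same sentence that drops subjects without a rating at the time point raises the relief percentages, whereas 11.7.1 counts such subjects as not pain-free. The net difference between the two tables is undetermined. Only the effect of the baseline-none subjects, taken alone, has a known direction.

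**A reader might infer that every companion analysis leaves these subjects out.** The first-dose time-to-event analyses keep them in the censored count, although they add nothing to the estimates. A curve of time to first relief need not match point-in-time proportions anyway.

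**A reader might infer a bias against lasmiditan at the second dose**, since an effective first dose makes zero pain more likely. SAP 4.1 limits this. Rescue requires pain at 2 hours, and recurrence requires that pain has returned. A subject pain-free at 2 hours without recurrence fits neither group and could appear only in an overall ITT-2nd Dose display. What remains is pain that resolved between qualifying and dosing, and nothing shows which sequences would have more of it. Nor do the documents give second-dose group sizes that would support a claim of large errors in small groups.

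**The size is probably small and the count is already reported.** Treating with no pain departs from the dosing conditions in both documents (Protocol 5.5, SAP 2.1) and excludes the subject from the per-protocol population (SAP 4.2), so a small first-dose share is plausible. SAP 8.5 shows the number with baseline none. Both points stand. However, 8.5 gives one overall count, while these denominators change by time point with missing ratings, and it does not mention a split by rescue and recurrence.

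**Conclusion.** The point holds as a minor inconsistency in the SAP. On the literal text, 11.7.5, 11.7.13 and 11.7.15 print p(1-q) where the SAP's handling elsewhere points to p. The relative loss equals q: 2% of the true rate at q=2% and 5% at q=5%. Both q and the 40% and 60% rates used to illustrate it are assumptions. There is no effect if no subject records none at the relevant baseline.

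At the first dose the consequence is mainly mild attenuation, provided q is similar across randomized arms. At the second dose q could differ by sequence, and the resulting distortion has no established direction.

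Only exploratory endpoints and the relief tables in the SAP 11.8 subgroups are affected. The primary and key secondary pain-free analyses exclude these subjects, the relief and second-dose endpoints lie outside the testing sequence in SAP 11.1, and the sample size is not involved.

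**What to change.** In SAP 11.7.5, 11.7.13 and 11.7.15, add one sentence restricting the denominator to subjects with headache severity of at least 1 at the relevant baseline: first dose for 11.7.5, second dose for the other two. This matches the subjects used in 11.7.1, 11.7.14 and 11.7.16. Footnote the number excluded for severity 0, by treatment group or sequence. The relief tables in SAP 11.8 should follow the same rule.

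The cost is one sentence in each of three sections and slightly smaller denominators. No new data are needed. The sentence should be added before unblinding, so that the choice cannot depend on results.

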11.7.6 Time to Headache Pain-Free

The time to headache pain-free will be presented by treatment group using a Kaplan-Meier analysis. This summary will be presented for the ITT population, based on the first dose.

The number of subjects experiencing headache pain-free, and the number of subjects censored, will be summarized. The Kaplan-Meier estimates, and 95% confidence intervals calculated using the log-log transformation, of the number of hours for 25%, 50%, and 75% of subjects to experience headache pain-free will be presented. The Kaplan-Meier estimate, and 95% confidence interval, of the probability of experiencing headache pain-free will be presented at the 0.5, 1, 1.5, 2, 3, 4, and 24-hour post-dose time points.

Time to headache pain-free will be calculated as:

date/time headache severity is reported as none (0) –
date/time of dosing of mild (1), moderate (2), or severe (3) headache

Subjects who do not report a headache with severity of none, or who report a headache with a severity of none after 24 hours post-dose, will be censored at the time of their last non-missing post-dose headache severity assessment at or before 24 hours. Subjects with missing baseline headache severity, or who report a headache severity of none (0) at baseline, will be censored at the time of first dose.

A figure of the Kaplan-Meier analysis will also be presented.

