## 5.2 Secondary objectives

To explore the time course and effect of lasmiditan 50 mg, of lasmiditan 100 mg and of lasmiditan 200 mg on relief of pain and on the MBS.

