### 9.1.8 Subject Diary

Subjects will be trained on the use of the electronic diary at **Screening/Visit 1**. Efficacy data will be collected in an electronic diary for an attack. Subjects will record the date and time at which their migraine headache starts and when it first becomes moderate or severe. They will also record the date and time of taking the first dose of study drug.

Subjects will be asked to assess their headache severity at specified time points: 0 (pre dose), 0.5, 1, 1.5, 2, 3, 4 and 24 and 48 hours post dose using the IHS four point headache severity rating scale (0 = no pain, 1 = mild pain, 2 = moderate pain, and 3 = severe pain). The need for rescue medication and second dosing of study drug or an alternative treatment will be assessed between 2 and 24 hour and at 48 hours. Recurrence of pain and second dosing of study drug will be assessed between 2 and 24 hours and at 48 hours.

At the same time points, 0 (pre dose), 0.5, 1, 1.5, 2, 3, 4, 24 and 48 hours, subjects will grade the degree of interference with normal activities and the presence or absence (yes or no) of accompanying symptoms: photophobia, phonophobia and nausea. At time 0 (pre dose) subjects will select from the accompanying symptoms present (nausea, phonophobia or photophobia) which one is the most bothersome to them. Subjects will be asked to record the presence or absence (yes or no) of vomiting. Subjects will also be asked to record the exact time at which headache relief became meaningful to them and the time at which they become headache pain free. At 2 hours subjects will be asked to record their global impression of change using a 7-point scale (very much better, much better, a little better, no change, a little worse, much worse, and very much worse).

The diary will also be used to record any symptoms or side effects the subject is experiencing and the use of any concomitant medications from **Visit 1** through to **EoS/Visit 2**

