 - The time intervals are 30 minutes, 1 hour, 1.5 hours, 2 hours, 3 hours, 4 hours, 24 hours, and 48 hours after the first dose of study medication. The e-diary sets the post dose assessments based on the recorded time of dosing. A subject that begins reporting their migraine at the exact time of dosing will have all of the post dose assessment time points available to them. If a subject starts recording their information in the e-diary after they dose including the time of dosing, the assessments that become available for them are based on the time of dosing, relative to when they accessed the e-diary. For example, if at 1-hour post actual dosing the subject initiates migraine mode and begins entering data into the e-diary, the subject will be allowed to respond to the initial questions about their migraine and time of dosing and then based on the time they record for dosing they automatically will miss subsequent time points, i.e.; the 30 minute and 1-hour time points. A missed time point is missed.
 - Alarms occur at the predefined time points to remind the subject it is time to complete the assessments. The Migraine Questions button is always available, but the subject is not be able to answer the questions until prompted by an alarm within a study migraine.
- Migraine Mode – Second Dose (Optional)
 - The subject should only take a second dose of study medication if the migraine pain is not gone by two hours after the first dose or the migraine pain was gone and came back two hours or more after the first dose (up to 24 hours after first dose).
 - The Dose 2 button will appear AFTER the e-diary recognizes 2 hours have passed since the first dose and remains until the 24-hour time point.
 - During the 2-hour post dose assessment the subject will be asked to indicate if he/she would like to take a second dose of study medication
 - If a second dose is reported alarm intervals are the same as for the reporting of the first dose and any remaining alarms from the first dose are cancelled. However, if

the subject inadvertently enters a dosing time of the second dose occurring prior to the first dose the first dose alarms do not stop and subject can therefore response to post-dose assessments based on time of dosing of first dose, therefore not really assessing their response to the second dose.

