11.7.14 Time to Headache Pain-Free After Second Dose

The time to headache pain-free after second dose will be presented by treatment sequence using a Kaplan-Meier analysis. This summary will be presented for the ITT-2nd Dose population, and separately for subjects taking a second dose for rescue or recurrence.

The number of subjects experiencing headache pain-free, and the number of subjects censored, will be summarized. The Kaplan-Meier estimates, and 95% confidence intervals calculated using the log-log transformation, of the number of hours for 25%, 50%, and 75% of subjects to experience headache pain-free will be presented. The Kaplan-Meier estimate, and 95% confidence interval, of the probability of experiencing headache pain-free will be presented at the 0.5, 1, 2, 4, and 24-hour post second dose time points.

Time to headache pain-free after second dose is calculated as:

- date/time headache severity is reported as none (0) after second dose –
- date/time of second dosing of a headache that was mild (1) or moderate (2) or severe (3) at

baseline

Subjects who do not report a headache severity of none after dosing, or who report a headache with a severity of none after 24 hours post second dose, will be censored at the time of their last non-missing post second dose headache severity assessment at or before 24 hours. Subjects with missing second dose baseline headache severity will not be considered in time to event analysis for second dose. Subjects who report a headache severity of none (0) at second dose baseline, will be presented in a separate listing as a report at the time of second dose. Subjects who report headache severity of mild (1) or moderate (2) or severe (3) at second dose baseline, will be considered in time to event analysis for second dose.

A figure of the Kaplan-Meier analysis will also be presented.

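### Time to pain-free is dated by prompted ratings with none between 4 and 24 h, so ordinary Kaplan-Meier will place any quartile in that gap at about 24 h or leave it non-estimable

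*SAP*

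**What the plan says.** - **Event and summaries.** SAP 11.7.6 measures from dosing to the "date/time headache severity is reported as none (0". Kaplan-Meier estimates "of the number of hours for 25%, 50%, and 75% of subjects to experience headache pain-free will be presented", with confidence limits. The same section asks for Kaplan-Meier probabilities at 0.5, 1, 1.5, 2, 3, 4 and 24 h, and a figure. SAP 11.7.14 uses the "date/time headache severity is reported as none (0) after second dose".
- **Rating schedule.** Protocol 9.1.8 schedules severity ratings at "0 (pre dose), 0.5, 1, 1.5, 2, 3, 4 and 24 and 48 hours post dose". SAP 5 gives the same post-dose prompts: "30 minutes, 1 hour, 1.5 hours, 2 hours, 3 hours, 4 hours, 24 hours, and 48 hours after the first dose". It adds that the questions cannot be answered before an alarm. After a second dose, Protocol 9.1.8.1 and 9.1.8.2 list 0.5, 1, 2, 4, 24 and 48 h, while SAP 5 repeats the first-dose intervals. Either way, nothing lies between 4 and 24 h.
- **The 24 h boundary.** Under SAP 11.7.6, a rating of none given later than 24 h after dosing is not an event. The subject is censored at the last rating at or before 24 h. SAP 5.4 and 11 say assessment times are used as the e-diary calculates them.
- **A second source.** Protocol 9.1.8 also has subjects record "the exact time at which headache relief became meaningful to them and the time at which they become headache pain free". No SAP section analyses the pain-free time; SAP 11.7.19 uses only the meaningful-relief question. SAP 5.1, which lists changes from the protocol, does not mention the omission.

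**The concern.** A Kaplan-Meier curve steps only at recorded event times. A subject who becomes pain-free at 5 h and stays so is first able to report it at 24 h, and the estimator treats 24 h as the exact time. The true information is only that the event lies between 4 and 24 h. A quartile in that interval then describes the alarm schedule, and two arms with quite different quartiles in the gap would show the same number.

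The protocol's secondary objective is "To explore the time course and effect of lasmiditan 50 mg" and the other doses on pain and the most bothersome symptom. The quartiles are a planned summary of that time course, and a reader would take a printed median of 24 h at face value. The same prompts feed SAP 11.7.7 and 11.7.8 (headache relief, MBS-free) and their second-dose counterparts 11.7.16 and 11.7.18.

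**Working it through.** The plan states no expected median or quartile, so there is no figure to reproduce. The core of the point needs no model; the model below only illustrates its size.

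**Step 1: the estimator.** The reported p-quantile is the first event time at which the estimated survival S(t) is at or below 1 − p. After the first dose, events up to 24 h can occur only at 0.5, 1, 1.5, 2, 3, 4 and 24 h. If fewer than a proportion p are pain-free by 4 h and at least p by 24 h, the reported quantile is 24 h wherever the true one lies between. A second dose adds no first-dose prompt: SAP 5 cancels the remaining first-dose alarms, and SAP 5.2 ends first-dose data at the second dose.

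**Step 2: constant-hazard illustration.** The inputs are the 2 h pain-free rates in Protocol 10.1 and SAP 2.2. The constant hazard is an assumption. Hazard h = −ln(1 − p)/2; median = ln 2/h; pain-free by t hours = 1 − exp(−ht). For placebo, h = −ln(0.926)/2 = 0.0384 per hour and the median is 0.693/0.0384 = 18.0 h.

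| Arm | 2 h rate | h per hour | By 4 h | By 24 h | True median | Reported |
|---|---|---|---|---|---|---|
| Placebo | 7.4% | 0.0384 | 14.3% | 60.3% | 18.0 h | 24 h |
| 50 mg | 13.9% | 0.0748 | 25.9% | 83.4% | 9.3 h | 24 h |
| 100 mg | 13.6% | 0.0731 | 25.4% | 82.7% | 9.5 h | 24 h |
| 200 mg | 18.8% | 0.1041 | 34.1% | 91.8% | 6.7 h | 24 h |

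In this case a placebo-to-200 mg difference of 18.0 − 6.7 = 11.3 h is reported as zero. The placebo 25% time (7.5 h) and the active 75% times (18.5, 19.0 and 13.3 h for 50, 100 and 200 mg) also become 24 h. Quartiles before 4 h only move to the next prompt, for example 2.8 h to 3 h at 200 mg.

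**Step 3: other shapes.** Pain-free times were simulated from Weibull distributions matched to the same 2 h rates, with 200,000 subjects per arm, and recorded at the first prompt. Medians are shown as true → reported:

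| Shape | Placebo | 50 mg | 100 mg | 200 mg |
|---|---|---|---|---|
| 0.7 (decreasing hazard) | 46.3 h → not reached | 17.9 → 24 h | 18.5 → 24 h | 11.1 → 24 h |
| 1.0 (constant) | 18.0 → 24 h | 9.3 → 24 h | 9.5 → 24 h | 6.7 → 24 h |
| 1.3 (increasing) | 10.9 → 24 h | 6.5 → 24 h | 6.6 → 24 h | 5.0 → 24 h |

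At shape 0.7 the proportions pain-free by 24 h are 35.5%, 57.4%, 56.5% and 69.5%, so placebo never reaches 50%. Letting a random 40% of those not pain-free at 2 h take a second dose (an assumption) changed none of the reported quartiles.

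**Step 4: the 24 h boundary.** Answers to the 24 h alarm come at or after 24 h. If actual answer times are used and answers after 24 h are censored back to 4 h, no arm has an estimable median at any of the three shapes.

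**The case against.** The strongest reply is that little depends on these quartiles. The endpoint is exploratory (SAP 3.3), SAP 11.7.6 names no log-rank test or other treatment comparison, and the same section gives probabilities at the scheduled times. SAP 11.7.1 adds pain-free proportions through 48 h. These show how the doses separate, and the gap does not distort them. This stands, and it limits the point to the quartiles.

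A reader might infer that every arm's median will read 24 h and that a placebo-to-200 mg difference of about 11 h will vanish. The documents do not support that as a prediction. They give 2 h rates only, and carrying those to 24 h extrapolates twelvefold in time. At shape 0.7 the placebo median is not reached, so placebo and 200 mg would not read the same.

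A reader might also infer that the diary holds an exact pain-free time ready to replace the ratings. The protocol attaches the word exact to meaningful relief. The SAP's diary description never mentions a pain-free-time item, so its completeness is unknown. If it is entered at the 24 h prompt, it relies on recall over up to 20 h, and a check that it falls between 4 and 24 h excludes little. SAP 5.4 describes retroactive, future and AM/PM errors in times that subjects enter. Preferring prompted ratings for the main analysis is therefore defensible. Treating them as exact event times is not.

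Finally, interval-censored estimation cannot locate a median inside a 20 h interval. That is true, and an honest output should show it.

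**Conclusion.** The point holds for quartiles that truly fall between 4 and 24 h. As written, SAP 11.7.6 and 11.7.14 will report them as about 24 h, or as non-estimable if late answers to the 24 h alarm are censored. This follows from the event definition, the prompt schedule and the estimator. Reporting at 24 h also assumes nominal prompt times, which SAP 5.4 and 11 support but 11.7.6 does not state.

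The number of arms affected is not known in advance. In the illustrations it is all four medians at shapes 1.0 and 1.3, and the three active medians at shape 0.7. The hours shown are illustrative.

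The 2 h primary and key secondary analyses and all confirmatory conclusions are unaffected. The gap does not distort the scheduled-time probabilities, although the 24 h value keeps its meaning only if the 24 h prompt is counted at nominal time. This is a misleading planned summary of an exploratory endpoint and should be corrected.

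**What to change.** 1. In SAP 11.7.6, 11.7.7 and 11.7.8, and in 11.7.14, 11.7.16 and 11.7.18, treat each event as interval-censored between the last prompt without the event and the first prompt with it, using the Turnbull estimate.
2. Report a quartile that falls in the gap as the interval 4 to 24 h, not as a point value.
3. State that a valid answer to the 24 h prompt counts as nominal 24 h, so that it is not censored back to 4 h.
4. For 11.7.6 and 11.7.14, add a supplementary analysis using the diary-recorded pain-free time where it is present and lies between the bracketing prompts. Report how many subjects have a usable value in each arm (each treatment sequence for the second dose).

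The cost is SAP wording and a little extra programming, with no change to data collection under the protocol. The stated quartiles will be wider, and the supplementary analysis carries recall error. If the recorded time proves too incomplete to analyse, items 1 to 3 still correct the output.
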